4. INFORMATION SOURCE

The information will be obtained from the data collected during the clinical visit, as well as from the data recorded by the patients themselves and the self-administered scales of the Questionnaires and Data Collection Notebooks that the researchers will deliver / administer. The researcher will be responsible for the study data being registered in the electronic CRD (eCRD).

5. SCOPE WHERE THE STUDY IS PERFORMED

National urology / nephrology consultations.

6. STUDY DESIGN

6.1 Type of study

Clinical trial with medical device (Lit-control®pH Meter device). Multicenter, prospective, randomized, double-blind, placebo-controlled study in adult patients who come to the urology / nephrology clinic who have recently had a double J stent or have their placement programmed and who are able to take charge of the urinary pH control at home.

They will be randomized into two groups (experimental group (Lit-control®pH Meter + food supplement Lit-control®pH Down) and control group (Lit-control®pH Meter + Placebo)). The ratio will be 1: 1 between the experimental group and the control.

In accordance with the current Royal Decree 1090/2015, of December 4, which regulates clinical trials with medicines, the Research Ethics Committees with medicines and the Spanish Registry of Clinical Studies, 18 a new type is contemplated a "low level of intervention" test in which less rigorous standards are adopted in aspects such as monitoring, the content of the master file or traceability, without impairing the safety of the individuals who participate in them. This concept was introduced by Regulation (EU) No. 536/2014 of the European Parliament and of the Council of April 16, 2014,¹⁹ which quotes verbatim:

"The risk to the safety of the test subjects comes mainly from two sources, the investigational drug and the intervention, but many clinical trials pose an additional risk to the safety of the subjects that is minimal compared to that of clinical practice. habitual. This is so, specifically, when the investigational medicinal product already has marketing authorization, which means that its quality, safety and efficacy were already evaluated during the authorization procedure or, if that medication is not used in accordance with the conditions of the marketing authorization, when its use is based on evidence and is supported by documented scientific data on the safety and efficacy of that medicine, and the intervention only involves a very limited additional risk for the test subject, compared with that of the practice usual clinic. "

In the same regulation, a "low-level intervention clinical trial" is defined:

- a) investigational drugs, excluding placebos, are authorized;
- b) according to the protocol of the clinical trial:
 - i. the investigational drugs are used in accordance with the terms of the marketing authorization, or
 - ii. the use of investigational medicinal products is based on evidence and is supported by published scientific data on the safety and efficacy of such investigational medicinal products in one of the Member States involved, and
- c) complementary diagnostic or follow-up procedures involve a risk or additional burden for the safety of the subjects that is minimal compared to that of usual clinical practice in any of the Member States involved.

In the present study, the condition of "low level of intervention" is requested since both products are phymeter (Lit-control® pH Meter) and food supplement (Lit-control®pH Down), marketed and represent a minimum risk for safety of the patient. The Lit-control® pH Meter medical device is a proven and validated safety and efficacy device for the determination of urinary pH, the use of which does not imply any risk for the user. On the other hand, hygienic-dietetic measures are a recognized and recommended intervention to decrease urinary pH, but

given the difficulty of introducing drastic changes in the diet effectively, this essay aims to study the effect of dietary supplementation, which implies a minimum intervention level and a practically zero risk for the patient.

The recommended dose of the Lit-control®pH Down food supplement is 2 capsules daily, but taking into account the recommended daily consumption according to the European Food Safety Authority (EFSA) of the components of Lit-control®pH Down, it could be extended to a maximum dose of 6 capsules daily, the "limiting factor" being the daily intake of zinc. A total of 3 capsules would correspond to 4.3 mg / day of elemental zinc, this being an amount within (below) the recommended daily requirements 7.3 mg / day and 5.5 mg / day for men and women respectively and it would be far from the NOAEL established at 50mg / day by the same ESFA from the available studies^{20,21}. Similarly, the limit for the prolonged zinc supply of > 25 mg established by the ESFA in which it must be specified on the label of the product that can produce anemia is also a value well above the daily intake proposed for the patients of the study²².

With the data mentioned above and based on the available evidence, the appropriate dose for the patient profile of the trial has been estimated at 3 capsules daily to be able to reach adequate doses of L-Methionine (the component responsible for acidification of urine) compatible with the therapeutic dose of 1500 mg / day observed in previous studies. In addition, this is the recommended dose according to the EAU guidelines on diagnosis and conservative management of urolithiasis¹³ to acidify urine. In the section of the justification of this protocol the discussion on this point is extended.

6.2 Study population

Adults who come to the urology / nephrology clinic who have recently had a double J stent or who have scheduled their placement and who are able to take charge of the urinary pH control at home.

6.2.1 Inclusion criteria

- Age ≥18 years.
- Patients who have recently had a double J stent (time less than a week) or who have scheduled their placement and are recommended to control the pH to avoid scaling / calcification.
- Patients who agree to participate in the study and provide their informed consent.

6.2.2 Exclusion criteria

- Patients with basic pathologies that, according to the researcher's criteria, are not susceptible to the recommendation of the food supplement object of study.
- Patients who have scheduled the extraction of the double J stent before 3 weeks from the baseline / inclusion visit.
- Uric and cystinuric patients that require pH control different from that established in the study protocol.

6.2.3 Discontinuation criteria

- Withdrawal of informed consent.
- Violation of the protocol.

- Patients with early withdrawal of the double J stent (time less than 3 weeks after the baseline visit).
- Use of other food supplements not specified in this protocol that could interfere with the evaluation of the efficacy of the supplement under study.
- Serious Adverse Event (AAG).
- Abandonment of the study.

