6.3 Observation period

6.3.1 Inclusion period

The urologist / nephrologist will recruit patients as they come to the consultation and meet the inclusion and exclusion criteria, according to the consecutive sampling technique. The assignment of the study treatment will be carried out randomly, according to the previously established code that will be assigned to each patient as they are included in the study.

The expected duration for the recruitment of patients will be 3 months with a follow-up period until the stent is extracted, which is expected to be a maximum of 2 months. The recruitment of the participating centers will be competitive.

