6.3.3 Baseline Visit - V0 (inclusion)

The researcher will consecutively include the patients as they come to their consultation. The investigator will inform the patient about the study and will provide the information sheet. In case the patient agrees to participate in the study, they must sign the informed Consent Form that the researcher will also provide. Subsequently, the researcher will ensure that the patient meets all the inclusion / exclusion criteria and proceed to confirm their inclusion in the study. If the patient is eligible but does not give informed consent and / or does not meet any of the inclusion / exclusion criteria, then the investigator will add a new case to the list of eligible patients without recording any other information related to the patient.

Sociodemographic data and medical and family history of interest will be recorded, as well as the date and reason for stent placement. The data will be recorded necessary to classify patients according to the "Blockage risk factor" 23. In addition, a urine test of 2 hours fasting will be requested.

At the end of the visit, the patient will be given the treatment assigned by randomization and the link to the electronic domicile CRD and on paper. The patient will be reminded that at the next visit they should return (empty or not) the blisters of the treatment administered.

NOTE: For reasons derived from the logistics and the tests to be performed with the stent, researchers should try to enter the data in the online CRD in real time (or within a 24 hour timeframe) both at the time of placement of the stent as of extraction. This will allow a follow-

up and an appropriate time of logistical management that guarantees that the stents arrive in optimal conditions for their study to the specialized center of Palma de Mallorca.

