6.3.4 Visit Final Control - Vf (stent removal)

The time of the final visit will not be determined by protocol but according to the moment in which, by usual clinical practice, the double j stent is extracted in a programmed manner (which should be between 3 and 8 weeks after the baseline visit). During this visit, the data regarding the symptoms perceived by the patient during the time with the stent will be recorded, data relative to the received treatment (adherence, presence of adverse effects, date of beginning and end of the pH control, complications derived from the stent and data on stent removal (date, complications, presence / degree of calcification, etc.) and this will be sent (after conditioning) * to be analyzed by an expert to determine the presence of any of the different stages of calcification (presence of bacterial biofilm, incrustations and / or calcifications.) During this visit, the patient will deliver his / her home diary with the pH control data and annotated supplement record (as long as it has not already been registered directly with the home eCRD) and will also transfer the product excess (food supplement blisters) and, if possible, also empty blisters.

On the other hand, pharmacoeconomic data will also be recorded in order to determine the cost-effective profile of the intervention.

* The conditioning of the stent for storage and subsequent delivery to the specialist who is going to carry out his study is described in the Investigator's Manual.

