6.6 Concomitant treatments

The existence of concomitant treatments will be recorded. Only those treatments likely to influence the results of the trial will be grounds for withdrawal from the study (see section 6.2.4).

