7 VARIABLES AND MEASURING INSTRUMENTS

7.1 Main valuation variables

- Score on the scale of incrustation (main variable of effectiveness):
 - or 0 (Without inlay).
 - or 1 (Sporadic calcifications less than 1-2 mm²).
 - or 2 (Calcifications of wide areas greater than 1-2 mm²).
 - or 3 (Complete block).
- Urinary pH level and control of it below 6.2 (urine 2h fasting and home self-control with Lit-control®pH Meter).
- Reason for stent placement (approximately 90% is expected to be urolithiasis).
- Obstruction risk factor²³.
- Stent analysis / observation (presence of biofilm, degree of incrustation).
- Double J stent study:
 - o Scanning electron microscopy + micro-analysis by dispersive energy of RX: type and size of the crystals formed.
 - or ICP-AES spectroscopy (degree of global calcification of each end: Ca, Mg and P).
- Presence (Yes / No) and Degree of calcification (I-V) (Annex 7) ²⁴.

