11.4 Follow up with AA

Patients can be withdrawn from the EC at any time. Patients withdrawn from the study due to an AA should be followed up by the investigator until the clinical outcome of the AA is determined.

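### Nothing requires the stent of a discontinued patient to be kept and scored, so a primary outcome that exists can be lost after randomisation

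*Protocol*

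**What the plan says.** The primary variable in section 7.1 is "Score on the scale of incrustation (main variable of effectiveness", graded 0 to 3 on the stent.

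Section 6.2.3 gives the discontinuation criteria. One is "Patients with early withdrawal of the double J stent (time less than 3 weeks after the baseline visit". Others are protocol violation, use of supplements outside the protocol, a serious adverse event, abandonment and withdrawal of consent. Assigned product is handed over at the end of the baseline visit (6.3.3), so these events can all fall after randomisation.

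Section 6.6 speaks of leaving the study, not just the product: "Only those treatments likely to influence the results of the trial will be grounds for withdrawal from the study". It refers to a section 6.2.4, which does not exist; the list is in 6.2.3.

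The instructions to record calcification and send the stent to the expert stand in section 6.3.4, the final visit, described as the point where "the double j stent is extracted in a programmed manner (which should be between 3 and 8 weeks after the baseline visit". After withdrawal, the only follow-up required is in section 11.4, and it concerns the adverse event: "Patients withdrawn from the study due to an AA should be followed up by the investigator".

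Other text points the other way. Section 6.3.1 describes recruitment "with a follow-up period until the stent is extracted", section 6.3.4 leaves the timing of the final visit to usual practice, and the logistics note in 6.3.3 asks for prompt data entry "both at the time of placement of the stent as of extraction", with no exception for early removal.

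**The concern.** A site reading 6.2.3, 6.6 and 6.3.4 together could reasonably conclude that a discontinued patient has left the study and that the stent need not be sent. Early removal is the clearest case, because the event that discontinues the patient also produces the specimen. Patients discontinued for a serious adverse event, a violation or a supplement will still have a stent removed later, and nothing says that it must be scored.

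The loss need not be random. Section 6.2.2 excludes at entry only "Patients who have scheduled the extraction of the double J stent before 3 weeks from the baseline / inclusion visit". Early removals under 6.2.3 therefore arise later: some may follow stent complications, others may be ordinary rescheduling. If the reason is related to encrustation, the scored stents are a selected subset of those randomised. This has to be settled in the protocol, because an analysis plan can choose among collected data but cannot recreate a stent.

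**Working it through.** **1. The plan's own figures.** Section 6.8 gives Mann-Whitney, effect size 0.6, 80% power, 94 patients, raised to 105 for 10% loss. Alpha is not stated; two-sided 0.05 is assumed here.
- t-test sample size at d = 0.6: 44.59 per arm.
- Divided by the Mann-Whitney efficiency 3/π = 0.955: 46.7, so 47 per arm, or 94.
- 94 / 0.9 = 104.4, so 105.

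Both figures reproduce. The sample size is not in question.

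**2. Illustrative model (assumed).** The protocol gives no score distribution, no early-removal rate and no link between removal and score.
- Control scores 0/1/2/3: 50/30/15/5%. Mean = 0.30 + 2×0.15 + 3×0.05 = 0.75; SD 0.887.
- Active: the same cut-points on a normal scale, shifted by 0.738, give 77.0/17.3/4.9/0.9%. Mean 0.296; SD 0.597.
- Difference = 0.75 − 0.296 = 0.454. Standardised: 0.454 / √((0.887² + 0.597²)/2) = 0.60, the plan's effect size.
- 52 active and 53 control; tie-corrected Mann-Whitney without continuity correction; 100,000 simulated trials per scenario.

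Share of patients scoring 2 or 3: (52×5.7% + 53×20%)/105 = 12.9%. Losing 10%, 25% or 50% of these removes 1.3%, 3.2% or 6.5% of all patients, inside the planned 10% loss.

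Example, 25% of scores 2-3 lost in both arms:
- Control mean = (0.30 + 2×0.1125 + 3×0.0375)/0.95 = 0.671.
- Active mean = (0.173 + 2×0.0364 + 3×0.0064)/0.986 = 0.269.
- Difference 0.402 instead of 0.454.

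| Stents not scored (same rule in both arms) | Patients lost | Mean difference | Power |
|---|---|---|---|
| None | 0% | 0.45 | 86.3% |
| 10% of scores 2-3 | 1.3% | 0.43 | 84.7% |
| 25% of scores 2-3 | 3.2% | 0.40 | 81.5% |
| 50% of scores 2-3 (extreme) | 6.5% | 0.34 | 74.5% |
| 5% of scores 0-1 | 4.4% | 0.46 | 85.7% |
| 10% of scores 0-1 | 8.7% | 0.47 | 84.6% |
| Unrelated to score | 3 / 6 / 10% | 0.45 | 85.4 / 84.3 / 82.8% |

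With no true effect, type I error is 4.9% to 5.0% under the score-related losses above.

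**3. Loss that differs by arm.** A separate null example assumes scores 40/35/20/5% and 52 per arm. If one arm loses 40% of its scores 2-3 and every other stent is lost at 5%, type I error is about 10%; with 20% it is about 5.7%. Under the null with blinding, removal driven by encrustation would not produce such a difference, so this marks an outer bound and is not an expectation.

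**4. The cost of including early stents.** If the analysis plan put short-dwell stents in the main analysis:

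| Early removals | Included, no effect in them | Included, half effect (latent shift halved) | Included, all score 0 | Left out |
|---|---|---|---|---|
| 3% | 83.9% | 85.5% | 84.9% | 85.4% |
| 6% | 81.4% | 84.3% | 83.0% | 84.3% |
| 10% | 77.3% | 82.7% | 80.2% | 82.8% |

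**The case against.** The strongest reply is that the text already covers early removal. Section 6.3.2 treats extraction and the final visit as one event, the heading of 6.3.4 does the same, and that section leaves the timing to practice and says only that 3 to 8 weeks is what should happen. On that reading any removal is the final visit, with grading and dispatch. Section 7.2 already lists the removal date. The Investigator's Manual, not available here, might say which stents to ship. The 3-week limit is used consistently and looks like a deliberate minimum exposure.

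The reading is possible for early removal, and for that reason the point is that stents can be lost, not that they will be. But 6.3.2 also sets 3 weeks as the minimum follow-up, 6.3.4 speaks of planned removal, and the reading does not help patients discontinued for other reasons before extraction. The protocol cites the Manual only for conditioning, storage and delivery. A minimum exposure may be a sound basis for an analysis set; it is no reason not to keep the specimen.

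Two further objections stand in part. The likely harm is modest: only the extreme case above falls below the planned 80%, and equal loss of high scores pulls towards no effect. And collection does not by itself raise power: including early stents that carry no effect costs up to about 6 points (82.8% against 77.3%).

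**Conclusion.** The concern holds as a gap in outcome collection, not as a demonstrated bias. The stated rules allow a randomised patient's primary outcome to go uncollected although the stent exists, and that loss is permanent.

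Its size cannot be determined from the protocol. Under the assumed distributions, score-related loss of 1.3% to 3.2% of patients costs about 2 to 5 points of power and reduces the difference from 0.45 to between 0.43 and 0.40. The extreme case costs about 12 points. Loss unrelated to score costs at most about 3.5 points at 10%. Type I error is not threatened unless loss differs between arms. These figures rest on the assumed score distributions, the assumed alpha and the assumed loss rates. The conclusion that nothing requires collection rests on the text alone. This is an inexpensive improvement worth making.

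**What to change.** State in 6.2.3 and 6.3.4, with matching wording in 6.6 and 11.4, that discontinuation under these criteria does not end outcome collection. For every randomised patient who has not withdrawn consent, the stent is collected, conditioned, shipped and scored whenever it is removed, and the date of and reason for removal are recorded. In the same edit, correct the reference in 6.6 to section 6.2.4.

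No stopping or removal rule changes, and whether short-dwell stents enter the main analysis or a sensitivity analysis is left to the analysis plan. The cost is a few sentences and a few more stents through the shipment route already planned. Stents of patients who withdraw consent stay outside the requirement, and some patients who abandon the study may remain out of reach.

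### Interfering supplements or treatments are grounds for withdrawal after randomisation but are not screened for at V0, which leaves an avoidable loss; a minor point, cheap to fix

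*Protocol*

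**What the plan says.** Two places in the protocol deal with products that could disturb the assessment.

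- Section 6.2.3 (Discontinuation criteria) lists "Use of other food supplements not specified in this protocol that could interfere with the evaluation of the efficacy of the supplement under study". The line is not limited to use that begins after V0.
- Section 6.6 (Concomitant treatments) first states "The existence of concomitant treatments will be recorded" and then "Only those treatments likely to influence the results of the trial will be grounds for withdrawal from the study (see section 6.2.4".

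The exclusion criteria in section 6.2.2 are three. The first concerns underlying conditions that, in the investigator's judgement, make the supplement unsuitable. The second concerns a stent removal planned less than 3 weeks after V0. The third reads "Uric and cystinuric patients that require pH control different from that established in the study protocol".

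The inclusion criteria in 6.2.1 cover age, a recent or scheduled stent with advice to control urinary pH, and consent.

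At V0 (section 6.3.3), "the researcher will ensure that the patient meets all the inclusion / exclusion criteria and proceed to confirm their inclusion in the study". The same section continues: "At the end of the visit, the patient will be given the treatment assigned by randomization".

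**The concern.** A condition that can be known at V0 is acted on only after randomisation. Neither the inclusion nor the exclusion list mentions products in use, and those lists are the only gate at V0. Recording concomitant treatments is not a gate.

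A patient who takes an interfering product at V0 and goes on taking it passes the check, receives a randomisation number and study product, and then meets 6.2.3 or 6.6. If withdrawn, the patient is a loss that one question before randomisation would have prevented. If kept, the patient's urinary pH may be driven partly by another product, which dilutes the comparison of pH and of incrustation.

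The two rules also differ in scope: 6.2.3 names food supplements only, 6.6 names treatments. Section 6.6 sends the reader to a section 6.2.4 for detail, but section 6.2 ends at 6.2.3 in both the table of contents and the body.

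**Working it through.** **Does any other provision close the gap?**

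| Provision | Catches a product in use at V0? |
|---|---|
| 6.2.2, first exclusion | No. It concerns underlying pathologies, at the investigator's judgement |
| 6.2.2, second exclusion | No. It concerns the date of stent removal |
| 6.2.2, third exclusion | Only incidentally. It is defined by disease, though it may remove some users of pH-modifying treatment |
| 6.3.3, V0 check | No. It refers back to the lists in 6.2.1 and 6.2.2 |
| 6.6, recording | No. It documents use and does not bar entry |

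The protocol handles a comparable matter at both points. A stent removal scheduled before 3 weeks is an exclusion in 6.2.2, and an actual removal before 3 weeks is a discontinuation criterion in 6.2.3. Interference appears only at the second point.

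**The plan's own sample size (section 6.8).** Inputs from the protocol: effect size 0.6, Mann-Whitney U test, power 80%, 10% loss, and 1:1 allocation (section 6.1). Section 6.8 states no alpha; two-sided 0.05 is assumed.

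- t-test: 44.59 per arm.
- Divided by the asymptotic relative efficiency of the Mann-Whitney test under normality, 3/π = 0.955: 46.69, rounded up to 47 per arm, 94 in total.
- Loss: 94 / (1 − 0.10) = 104.4, rounded up to 105.

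Both stated figures are reproduced. The allowance is 105 − 94 = 11 patients.

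**Effect of the gap.** Let w be the share of randomised patients withdrawn because of a product already in use at V0. The protocol gives no value, so 5% and 10% are assumptions.

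*Reading A: these losses come on top of the full 10%.* Evaluable N = 105 × 0.90 × (1 − w). Power = Φ(0.6 × √(n/2) − 1.96), with n = 0.955 × N/2.

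| w | Evaluable N | Power |
|---|---|---|
| 0 | 94.5 | 0.813 |
| 5% | 105 × 0.90 × 0.95 = 89.8 | 0.793 |
| 10% | 105 × 0.90 × 0.90 = 85.05 | 0.771 |

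The cost is 0.813 − 0.793 = 0.020 at 5% and 0.813 − 0.771 = 0.042 at 10%, about 2 to 4 percentage points.

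*Reading B: these losses are part of the 10%.* At w = 5%, 105 × 0.05 = 5.25, so about 5 of the 11 places are used and 94 is still reached if other losses do not exceed 11 − 5 = 6. At w = 10%, 105 × 0.10 = 10.5, which takes nearly the whole allowance.

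**The case against.** The case for leaving the text alone has several parts.

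- **The discontinuation line reads naturally as use during the study.** A patient who stops the product at V0 does not meet it. This stands: the problem needs a patient who continues the product and a product judged to interfere. It would be wrong to say that every prior user meets the withdrawal rule on the day of randomisation.
- **Frequency is unknown.** A reader might infer that prior use is likely because 6.2.1 asks for patients advised to control their pH. The documents do not support this. The advice is tied to a stent placed less than a week ago or still scheduled, so it may be as recent as the stent.
- **Section 6.8 does not limit the 10% loss by cause.** Withdrawals under 6.2.3 can fall inside it, so the drop to 90 or 85 is the less favourable of two readings. This stands.
- **Withdrawal need not mean a missing outcome.** The stent is removed in usual practice, and the protocol does not say that discontinued patients leave the analysis. This also stands, and it makes the figures above upper estimates for the assumed rates.
- **The reference to 6.2.4 most plausibly means 6.2.3**, and 6.6 is itself enough to withdraw a patient for an interfering medicine. That is fair: the dead reference is an editorial slip. It still leaves an investigator who follows it with nothing to read.

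None of this supplies the missing entry criterion.

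**Conclusion.** The gap is real and can be checked in the text: 6.2.3 and 6.6 act after randomisation on a condition that 6.2.2 does not screen for, and 6.6 cites a section that does not exist. Its consequence is limited to avoidable loss, or dilution if the patient is kept, among patients who use an interfering product at V0 and continue it.

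The size is uncertain and modest. It rests on assumed shares of 5% to 10%, an assumed two-sided alpha of 0.05, the 0.955 efficiency, and withdrawn patients not contributing to the analysis. The cost is at most about 2 to 4 points of power if these losses add to the full 10%, and less or none if they fall within it.

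A reader might also infer that the result would be biased between arms. The documents do not show that: use at V0 is a baseline condition, which randomised, double-blind allocation balances in expectation. This is a minor point with a cheap improvement.

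**What to change.** Reconcile sections 6.2.2, 6.2.3 and 6.6:

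1. Apply the protocol's existing interference criterion at V0, before randomisation, as well as during follow-up. This takes one line in 6.2.2.
2. Give 6.2.3 and 6.6 the same scope, so that supplements and treatments are covered alike.
3. Correct the reference to 6.2.4 in section 6.6.

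Which products count as interfering is for the sponsor to list.

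The planned 94 and 105 do not change. Concomitant treatments are already to be recorded, so little extra data collection is needed. The downside is that a few candidates are turned away before randomisation.
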